- d) Individuals from vulnerable populations (e.g., inmates [question #29], homeless [question #28], pregnant women [question #2], and those with auditory impairment [at the discretion of the Site Coordinators upon recruitment]). However, individuals who become pregnant or develop auditory impairments after they have been randomized to

study condition may remain in the study until completion. Additionally, individuals on probation will be considered eligible and their participation in the study will not interfere with their requirements of probation.

5. We will randomize participants (patients and caregivers) who meet the "eligibility criteria" and exclude from randomization participants based on the "exclusion criteria."

C. Randomized Controlled Trial (RCT) Design

Population: To estimate the population of participants, we obtained data on the number of patients who have been diagnosed with LC and HNC at DHHA, University of Colorado Hospital, NJH, and St. Mary's in a 3-year period (2012-2014) prior to the grant submission. The 4 sites had a population of about 1,211 LC and HNC patients who would be invited to participate in the study to complete "baseline measures," with about 70% of patients expected to meet criteria as being uninsured or underinsured patients. As **Figure 1** displays, the estimated sample is 848 patients (and 848 of their caregivers) expected to be eligible for randomization.

Participants who meet the "randomization inclusion criteria" will be randomized to condition by the database manager using the REDCap™ software at CU-Denver as follows:

- 1. Block randomization, adjusting for imbalance in patients' tumor site and stage of diagnosis in the analysis, will ensure an equal distribution of patients and caregivers across arms.
- 2. For patients and caregivers who both agree to participate in the study, they will be randomized together to the same condition (either "enhanced usual care" or "stepped-care intervention"). Per "baseline measures" of distress, patients and caregivers randomized to the "stepped-care intervention" will be assign to an intervention step based on their individual distress scores.

Randomization and sample size: Figure 1 shows the participants' random assignment to study condition.

[figure not shown]

Figure 1. The 444 participants expected to be randomized (222 LC and HNC patients and 222 caregivers)

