Of the 1,211 patients and 1,211 caregivers (2,422 participants) about 30% will refuse to participate, leaving 848 patients and 848 caregivers (n=1,696) to be screened for randomization. Of these, about 816 patients (47%-57%) will meet exclusion criteria) or refuse further participation (drop-out), based on average participation rates reported in other similar studies. 92 Thus, we estimate that about 444 participants (222 patients; 222 caregivers) will be randomized to one of 2-arms (or 222 per arm). About 44 participants in each arm might drop out of the study, have a member of the couple die, or be lost to follow-up (20% attrition), with 178 participants per arm to remain in the study for the analyses. Figure 1 shows a total of about 356 participants will be available for final analyses. This sample allows us to detect a 0.38 effect size with 90% power.

RCT Conditions/Arms

- Arm 1: Enhanced Usual Care: DHHA, St. Mary's, University of Colorado Hospital, and NJH hospitals provide supportive mental health care for patients such as printed materials, support groups, crisis counseling, and specialized care (e.g., psychiatric medication). Because the amount of usual mental health care that each patient receives varies at each site, we will standardize and monitor the usual care arm across the four sites with an enhanced usual care condition. All participants will receive upon enrollment a "Mental Health Resource Guide" with, (a) web links with mental health resources available at the national and local level, and (b) a list of support groups and mental health care providers to access if they encounter challenges. Participants in the baseline group and enhanced usual care, per usual care practices, with high levels of distress, suicidal ideation and needing specialized care (e.g., psychiatric medication, crisis counseling), will be referred to specialized mental health care following the established protocol at the hospital rather than provided access to the intervention.

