Sample size and power analysis: We estimated minimum effect sizes detectable for different power specifications for various sample sizes. Our target sample size for analyses is 290 patients and 290 caregivers (145 per arm) but we will recruit an initial sample of 222 patients and 222 caregivers (222 per arm) to allow for variability due to 24-34% attrition, based on attrition rates in meta-analyses ⁸⁸ and in our studies. ^{57, 59} If we had a smaller number of participants or if attrition was higher, we would need a minimum of 110 dyads per arm to still be able to detect small to moderate effect sizes. Power is assumed to detect a time by treatment interaction within the proposed repeated measures design. Correlation of measures across time points (rho) was specified as moderate (.4), although sensitivity analyses examined the minimum detectable effect size at alternative specifications of rho and still allow small to moderate effects. Power calculations are for 3 outcomes through a Bonferroni reduction of the significance level to alpha = 0.05/3 = 0.0167. The study is designed to minimize contamination between intervention and control groups (e.g., randomizing both patients and their caregivers to the same group, referrals based on usual care practices). Nevertheless, based on Torgerson, we conservatively powered the study to detect a smaller effect than anticipated in the event of potential contamination.

Analysis approach: Using an intent-to-treat (ITT) approach, primary and secondary outcomes will be analyzed with *linear mixed models* comparing the two groups (*stepped care intervention, usual care*) in patients and caregivers separately.

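### The sample-size figures contradict each other, and 90% power for 0.38 rests on patients and caregivers counted together although they are analysed separately

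*Combined protocol and SAP*

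**What the plan says.** Section IV.C (Randomization and sample size) starts from 848 patients and 848 caregivers, 1,696 in all, to be screened. It then says "about 816 patients (47%-57%) will meet exclusion criteria" or drop out, and that "about 444 participants (222 patients; 222 caregivers) will be randomized to one of 2-arms (or 222 per arm"). The caption of Figure 1 repeats the count: "The 444 participants expected to be randomized (222 LC and HNC patients and 222 caregivers"). Attrition of 20%, about 44 per arm, follows, "with 178 participants per arm to remain in the study for the analyses", and the power statement is made for that sample: "about 356 participants will be available for final analyses. This sample allows us to detect a 0.38 effect size with 90% power". Section I gives the same 816 and the same 222 of each role, but calls the 816 participants.

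Section IV.G (Sample size and power analysis) gives other figures: "target sample size for analyses is 290 patients and 290 caregivers (145 per arm) but we will recruit an initial sample of 222 patients". Caregivers are to be recruited in the same number, the label is again 222 per arm, and the stated reason is "to allow for variability due to 24-34% attrition". It adds that with fewer participants or higher attrition "we would need a minimum of 110 dyads per arm to still be able to detect small to moderate effect sizes".

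Section IV.G also fixes the analysis. Linear mixed models are fitted to patients and caregivers separately. Tests are two-tailed, with alpha 0.05/3 = 0.0167 for primary outcomes. Power refers to the time-by-treatment interaction over four assessments, with correlation 0.4 between time points. Maximum likelihood keeps participants with incomplete data.

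**The concern.** The power statement describes a sample that no planned model uses. If 178 per arm are participants, about half are patients and half caregivers, and each primary analysis has about 89 per arm. Separately, the stated numbers screened, randomised, lost and analysed do not follow from one another.

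The documents therefore support both about 222 and about 440 of each role as the number to randomise, a factor of two. Recruitment tracking, data-monitoring review and the reading of a null result all depend on that number. If 222 of each is meant, a null result in either role could be taken as evidence against an effect of 0.38 when the analysis had little chance of finding one.

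**Working it through.** **1. The plan's own figure.** Inputs: n = 178 per arm and effect 0.38 (section IV.C); two-sided alpha 0.0167 (section IV.G). Assumption: 0.38 is a difference in SD units, since the metric is not stated. For a simple comparison of two means:
- 0.38 x sqrt(178/2) = 3.585; 3.585 - 2.394 = 1.191; power 88% (0.883 normal, 0.880 t). This is close to the stated 90%.

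**2. The same test at the size of each analysis.** 222/2 = 111 per arm per role; 111 x 0.80 = 88.8, about 89.
- 0.38 x sqrt(89/2) = 2.535; 2.535 - 2.394 = 0.141; power 55% (0.556 normal, 0.548 t).

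**3. The planned interaction test, completers only.** Assumptions: time categorical (3 df), compound symmetry with correlation 0.4, and an effect either linear in time over 0, 6 weeks, 3 and 6 months (0, 1/4, 1/2, 1) or constant after baseline (0, 1, 1, 1). Noncentrality = (n/2) x sum of squared deviations of the effects from their mean / (1 - 0.4).
- Linear, n = 89: 44.5 x 0.1444 x 0.547 / 0.6 = 5.86, power 34%.
- Constant, n = 89: 44.5 x 0.1444 x 0.75 / 0.6 = 8.03, power 48%.
- With no attrition (n = 111): 44% and 61%.
- At correlation 0.6, n = 89: 53% and 71%.

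**4. The same test with partial data kept.** The noncentrality is now computed from the information contributed by each dropout pattern. With 111 per arm randomised and 20% monotone dropout, placed anywhere from all before 6 weeks to all before 6 months, power is 35-36% (linear) and 53-60% (constant).

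**5. Counts.**

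| Check | Result |
|---|---|
| 1,696 - 816 | 880, stated 444 |
| Loss needed to reach 444 | 1,252/1,696 = 74%, stated 47%-57% |
| 816 as participants (section I) | 816/1,696 = 48% |
| 816 as patients (section IV.C) | 816/848 = 96%, leaving 32 patients |
| Analysable from 222 of each at 24-34% attrition | 169 to 147 of each, stated target 290 |
| Randomised to analyse 290 of each at 24-34% attrition | 290/0.76 = 382 to 290/0.66 = 440 of each |
| Dyads per arm left from 222 of each at 20% attrition | about 89, stated minimum 110 |

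**6. Possible explanations.**
- Dyads per arm: 880/2 = 440 dyads, 220 per arm, close to 222. Then 440 x 0.66 = 290, the analysis target.
- Mislabelled participants: 444 x 0.66 = 293, so 290 could be a total of participants at 145 per arm.
- Figures left over from a previous version of the plan: 222 of each is 111 dyads per arm, almost exactly the stated minimum of 110.

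**7. Power if 222 per arm are dyads.** With 178 completers per arm in each role, the interaction test has 70-86%. With partial data kept at 20% attrition it has 72-93%.

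**The case against.** The strongest reply is that the power cannot be judged because neither the effect-size metric nor the contrast is defined. Part of this stands. At 89 per arm and correlation 0.4, the mean of three follow-ups has about 80% power and the baseline-adjusted mean about 92%. If 0.38 were Cohen's f (d = 0.76), the interaction test would have about 97% or more. But the first two are not the interaction that section IV.G says the study is powered for, and d = 0.76 does not fit that section's description of small to moderate effects.

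The 3 df and the two effect patterns are also assumptions. A transient effect (0, 1, 1, 0) would give 64.5% at 89 completers, and a 1-df slope test under the linear pattern about 51%. Both are still well short of 90%.

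Two stronger readings are tempting. One is that 90% for 0.38 was miscalculated. It was not clearly so: step 1 returns 88%. The other is that 222 per arm certainly meant dyads, so that about 440 of each were always intended. The arithmetic fits well, but sections I, IV.C and IV.G and the caption of Figure 1 all give 222 patients and 222 caregivers, two other explanations fit parts of the figures, and the figure itself is not visible. A dyad count would not settle the numbers by role either, because section IV.B lets a patient or caregiver take part alone.

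**Conclusion.** The contradictions in the counts stand without any statistical assumption, and neither the participant nor the dyad reading makes all the figures agree. The power statement does not describe the planned analyses. As literally written, each role has about 89 per arm after 20% attrition, with 55% power for 0.38 on a simple test. The interaction test has 34-48% with completers only, or about 35-60% with partial data kept. Those interaction figures assume SD units, 3 df, correlation 0.4 and an effect between linear in time and constant after baseline.

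A reader might infer that the trial is underpowered and must enrol more. The documents do not support that step: which number is the operating target is exactly what they leave open. This must be corrected, because a core design figure is stated in two incompatible ways.

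**What to change.** - In section I, section IV.C (including the caption of Figure 1) and section IV.G, state whether 222, 178, 145 and 110 are participants or dyads per arm.
- Make the exclusions, number randomised and number analysed agree, with patients and caregivers counted separately, and settle whether 816 means patients or participants.
- Use one attrition assumption.
- Define the effect size and the contrast it refers to.
- Replace the statement of 90% power for 0.38 by the effect detectable in each role, for the planned maximum-likelihood interaction test at the actual visit times.

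For illustration, at 90% power, alpha 0.0167, 3 df, correlation 0.4 and 20% attrition, from constant after baseline to linear in time:

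| Randomised per arm per role | Partial data kept | Completers only |
|---|---|---|
| 111 | about 0.51-0.65 SD | 0.57-0.66 SD (89) |
| 222 | about 0.36-0.46 SD | 0.40-0.47 SD (178) |

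If 222 of each is the operating target, restate the power and the 290 target and leave enrolment alone. The cost is wording and a less favourable stated figure. If about 440 of each was always intended, correct the stated number randomised wherever it appears. Moving from 222 to 382-440 of each would be a near doubling of enrolment, not an edit, and is not proposed here.

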A. Outcome Measures: We will utilize patient-reported outcome (PRO) measures that have been found to be valid and reliable, including with Spanish-speaking populations (see Table 1). To ensure that the measures are appropriate for low-literacy populations, a pilot test was conducted with our patient and caregiver stakeholders and items that were difficult to understand or to answer were simplified. Thus, we will further assess their validity and reliability in our sample. All consented study participants will be compensated \$25 to complete the measures at baseline ("baseline measures"), which will also include sociodemographic questions to determine "randomization inclusion and exclusion criteria." Only participants who are randomized to condition will complete the measures at 6-weeks, 3-months and 6-months from the date they completed the baseline measures and will be compensated \$25 every time.

Table 1. Patient-centered outcomes to be assessed at baseline, 6-weeks, 3-months, and 6-months

	Patients	Caregivers
PRIMARY OUTCOMES		
Depression & Anxiety	Hospital Anxiety and Depression Scale (14 items)	Hospital Anxiety and Depression Scale (14 items)
Depression	PROMIS-Ca Form v1.0 – Depression (30 items)	PROMIS Form v1.0 – Depression (28 items)
Anxiety	PROMIS-Ca Form v1.0— Anxiety (22 items)	PROMIS Form v1.0 – Anxiety (29 items)
Coping	Coping Self-Efficacy (26 items)	Coping Self-Efficacy (26 items)
SECONDARY OUTCOMES		
Health-Related	FACT-Lung Cancer version 4 (36 items)	
Quality of Life	FACT-Head-and-Neck Cancer (27 items)	
Perceived Stress	Perceived Stress Scale (PSS) (10 items)	Perceived Stress Scale (PSS) (10 items)
Caregiving Burden		Zarit Burden Interview (ZBI) (12 items)

The measures package takes about +/- 30 minutes to complete when it is *self-administered online* or via a *hard copy* but about 45 minutes when administered orally in person or over the phone. If a participant is unable to complete the measures online or express preference for a hard copy, they will be:

- (1) Mailed a copy of the measures and ask to return within 15 days of receipt. If after 15 days of the initial online request or if they expressed preference for an oral administration, they will:
- (2) Receive a phone call from a Graduate research assistants (GRA) who will administer the measure to participants by phone. If the GRAs are unable to locate the participants after 3 attempts (including leaving voice messages), they will

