Health-related Quality of Life: We will use the Functional Assessment of Cancer Therapy (FACT)⁷⁶ to measure health related quality of life. The FACT has been found valid and reliable among lung cancer (FACT-L, a=0.68-89) ^{77,78} and head-and-neck (FACT-HN, a=0.74-86) patients. ^{83,84} The FACT-L and FACT-HN incorporate the FACT plus additional symptom-specific items for LC and HNC. Items are rated on a 0 to 4 Likert type scale, and then combined to produce subscale scores and a global QoL score.

Perceived Stress: The Perceived Stress Scale (PSS) ⁸¹ will be used to measure *perceived stress*. This 10-item scale is scored on a 5-point Likert type scale to assess the degree to which situations are appraised as stressful. The PSS' internal consistency reliability range from 0.80 to 0.89 ⁸² and has been used among cancer patients ⁸³ and among caregivers of cancer patients. ⁸⁴

Caregiver Burden: The Zarit Burden Interview (ZBI) will measure caregiving burden. The 12 items ask caregivers to rate the impact that the patient's condition has had on the caregiver's life on a 5-point Likert-type scale. It provides an overall caregiver burden score, with higher scores indicating greater burden. The ZBI has good internal consistency reliability, with a Cronbach's alpha coefficient of .92.

Sociodemographic Characteristics at Baseline (including randomization inclusion and exclusion criteria): Demographic characteristics (not in Table 1) will be assessed at baseline with a self-report survey that includes participants' age, sex, place of birth, years living in the U.S., marital status, current and future employment status, education, and mental health history. For patients it will also include diagnosis and treatment questions, and for caregivers it will include questions about caregiving responsibilities. The survey will ask "randomization inclusion or exclusion criteria" questions to determine RCT eligibility:

- 1. Questions related to inclusion criteria will ask participants to report (a) what language they speak and read; (b) monthly income (after taxes); (c) how many people live at home that depend on the income reported; (d) health insurance status, including insurance type; and (e) estimated health insurance copays and deductibles (to estimate out-of-pocket costs).

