- 2. Questions related to exclusion criteria will ask participants to self-report (a) current or past impairments (cognitive and affective disorders) that make participants vulnerable to decision-challenges; (b) current suicidal ideation; and questions to assess if they belong to vulnerable populations (e.g., inmates, homeless, pregnant, deaf).

B. Description of the Methods to Enroll Participants in the Study

Participants will be recruited from four hospitals: the **Denver Health and Hospital Authority (DHHA)**, **University of Colorado Hospital** and **National Jewish Hospital (NJH)** in Denver, and **Saint Mary's Hospital and Medical Center (St. Mary's)** in Grand Junction. Each hospital will hire as their employee a Site Research Coordinator who will be trained to recruit and consent study participants (hospitals will cede to COMIRB's oversight of the research, including personnel training requirements).

- 1. We will pre-screen all cancer patients to identify recently diagnosed LC and HNC patients through various methods:
 - a. Monthly audit of electronic medical records from all hospitals to identified patients diagnosed with LC or HNC within 30 days prior to the audit.
 - b. Weekly attendance to cancer tumor boards to identify recently diagnosed patients.
 - c. Daily review of clinic visits to identify all LC and HNC patients in the oncology clinic, earnose-and throat (ENT) clinic, and radiation oncology clinic/unit at each hospital.
 - d. Recruitment flyers in English and Spanish will be used to advertise the study at each hospital site and via Social Media sites. The flyers instruct recently diagnosed LC or HNC patients and their caregivers to contact the Site Coordinator if interested in the study.

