- D. PHI for each participant will be kept unidentified in REDCap,™ to be identified by a numeric study code assigned to the participant upon being consented into the study (only the Site Coordinators as employees of the institutions will have access to identified information). The SRC will only record PHI on the diagnostic criteria (e.g., LC and HNC) from all prescreened individuals. The SRC will also record demographic data (e.g., age, gender, ethnicity, patient) to log recruitment efforts and for the DSMB to evaluate bias in recruitment, and for final analysis to determine demographics of individuals who were not included in the study.
- E. Each participant will be asked to provide, if possible, two phone numbers to deliver to them information related to their participation in the study (e.g., appointment reminders).
- 4. Using information collected from the "baseline measures" we will screen for "randomization inclusion and exclusion criteria," which includes the following criteria:

LC and HNC patients' randomization criteria [information in brackets refers to the question numbers that assess inclusion and exclusion criteria in the sociodemographic survey, attached]

Eligibility criteria:

- a) Recently diagnosed LC and/or HNC (within a month of recruitment date from the date of 1st visit oncology, ENT, or radiation clinic visit/consultation upon pathologic tissue diagnosis [question #14]
- b) LC and/or HNC patients at any stage of diagnosis (Stages 0-IV) [question #15];
- c) Over 18 years old; [question #1];
- d) English and/or Spanish speaking [questions #4];
- e) Medically underserved, as defined by at least one or several of the following:
 - a. Low-income: Below 400% of the 2016 Federal poverty levels 85,87 [question #10];

- b. Uninsured: No health insurance (public or private insurance) [question #9];
- c. Underinsured:
- (c.1) Public insurance (e.g., Medicaid, Medicare exclusive, VA) [question #9];
- (c.2) 10% of annual income on out-of-pocket medical expenses⁸⁶ for individuals below 200% of the 2016 Federal poverty levels [questions #9 and #10].

Exclusion criteria:

- a) Individuals who do not meet eligibility criteria, including individuals who do not speak English or Spanish [at the discretion of the Site Coordinators upon recruitment];
- b) Those who refuse treatment at one of four hospital sites.

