- c) Decisionally-challenged adults with cognitive or personality impairment [question #19 & #20a-c], suicidal ideation [question #30], or intoxication (alcohol or drugs) that might interfere with their ability to consent or participate in the study [at the discretion of the Site Coordinators upon recruitment or the Counselor during for the intervention];
- d) Individuals from vulnerable populations (e.g., inmates [question #29], homeless [question #28], pregnant women [question #2], and those with auditory impairment [at the discretion of the Site Coordinators upon recruitment]). However, individuals who become pregnant or develop auditory impairments after they have been randomized to study condition may remain in the study until completion. Additionally, individuals on probation will be considered eligible and their participation in the study will not interfere with their requirements of probation.

Caregivers of LC and/or HNC patients

Eligibility criteria:

- a) Primary caregiver of a recently diagnosed LC and/or HNC patient (per criteria for patients) [question #13];
- b) Over 18 years old [question #1];
- c) English and/or Spanish speaking [questions #4 and #5];
- d) Medically underserved, as defined by at least one or several of the following:
 - a. Low-income: Below 400% of the 2016 Federal poverty levels^{85, 87} [question #10]
 - b. Uninsured: No health insurance (public or private insurance) [question #9]
 - c. Underinsured:
 - (c.1) Public insurance (i.e., Medicaid, Medicare exclusive, VA) [question #9]
 - (c.2) 10% of annual income spent on out-of-pocket medical expenses⁸⁶ for individuals below 200% of the 2016 Federal poverty levels [*question #9 and 10*].

Exclusion criteria:

- a) Individuals who do not meet eligibility criteria, including individuals who do not speak English or Spanish [at the discretion of the Site Coordinators upon recruitment];
- b) Caregivers of patients who refuse treatment at one of four hospital sites.
- c) Decisionally-challenged adults with cognitive or personality impairment [question #19 & #20a-c], suicidal ideation [question #30], or intoxication (alcohol or drugs) that might interfere with their ability to consent or participate in the study [at the discretion of the Site Coordinators upon recruitment or the Counselor during the intervention];

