- Step 3: Coping Skills Training: (PROMIS score 60-69). ⁶³ Participants experiencing moderate levels of distress will receive the *Orientation Session*, the *Self-Help Guide*, and two *Coping Skills Training* sessions with the Counselor. Participants will learn problem-focused and emotion-focused coping strategies, ⁵⁴ and to identify controllable and uncontrollable stressors and how to match them to the appropriate strategy. Participants will practice the strategies between sessions.

Step 4: Cognitive-Behavioral Therapy (CBT): (PROMIS score >70).⁶³ Participants reporting high levels of distress, will receive the *Orientation Session*, the *Self-Help Guide*, two *Coping Skills Training* sessions, and four *CBT sessions*. The Counselor will introduce evidence-based CBT techniques, which focus on modifying the impact of stress via the interpretation of and reactions to stressors (cognitive and emotional reactions) and by correcting cognitive distortions. Participants who are not helped by the intervention or who require specialized treatment will be referred for services at the hospital, although they will continue to be included in the final analyses. If a patient dies, the caregiver may continue participating and will be moved to Step 4 to receive a grief session.

[figure not shown]

Figure 1. Stepped-Care Intervention Conceptual Framework to Assign Participants to a Step. 95

Referral Protocol: Participants (baseline group, enhanced usual care, and stepped-care intervention) will be referred to specialized mental health care if they endorse suicide ideation or substance abuse items during any of the assessment points (baseline, 6-weeks, 3-months and 6-months) or if they voice such issues to the Site Research Coordinator upon enrollment or to the Counselor during the intervention. If participants are not helped by the intervention or require psychiatric medication, they will be referred also to specialized mental health services per protocols already in place at the participating hospitals. During the study's 12-hour training, the Site Coordinators and Counselors will be instructed to follow their institution's protocol for suicidal ideation and other crisis (e.g., intoxication) to make referrals.

D. Description, Risks and Justification of Procedures and Data Collection Tools

Potential Risks

- a) Physical injury No known risks, but if there are risks they are likely to be rare and the magnitude low.

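### Referral relies on suicide-ideation and substance-abuse items at any of four assessments, but the documents identify no such item after baseline, and the gap is wider in enhanced usual care

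*Combined protocol and SAP*

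**What the plan says.** The Referral Protocol in Section IV.C covers the baseline group, enhanced usual care and the stepped-care arm. Participants are referred "if they endorse suicide ideation or substance abuse items during any of the assessment points (baseline, 6-weeks, 3-months and 6-months". A second route follows: "or if they voice such issues to the Site Research Coordinator upon enrollment or to the Counselor during the intervention".

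Section IV.A describes the survey that holds the suicide question: "Demographic characteristics (not in Table 1) will be assessed at baseline with a self-report survey". Among its exclusion-related questions is "b) current suicidal ideation". Section IV.B, item 4, explains its bracketed numbers: "information in brackets refers to the question numbers that assess inclusion and exclusion criteria in the sociodemographic survey, attached". Exclusion criterion (c), for patients and for caregivers, then lists "suicidal ideation [question #30], or intoxication (alcohol or drugs", so the suicide question is number 30 of that survey. Intoxication has no question number of its own and is left to the discretion of the Site Coordinator or the Counselor.

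The follow-up battery is set out under "Table 1. Patient-centered outcomes to be assessed at baseline, 6-weeks, 3-months, and 6-months". It comprises HADS, PROMIS depression and anxiety, coping self-efficacy, FACT, the Perceived Stress Scale and the Zarit Burden Interview. Only randomised participants complete it after baseline.

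The description of Arm 1 adds that enhanced usual care participants with suicidal ideation or a need for specialised care will be referred under the hospital's own protocol. It does not say how or when they are identified.

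**The concern.** The trigger takes for granted that certain items are answered at every assessment. The sections that define what is asked, and when, identify such an item only at baseline, and then only for suicidal ideation. Suicidal ideation is also an exclusion from randomisation. For randomised participants the trigger therefore does most of its work at 6 weeks, 3 months and 6 months, where no item is named.

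The main stake is participant safety. The plan's own background section says that lung and head-and-neck cancer patients tend to have higher suicidality than other cancer patients. A protection that staff cannot map to an item may be missed, or applied differently from site to site.

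A second stake is statistical. If ideation is easier to notice in the arm that has a Counselor, referral to specialised care could differ between arms because of detection alone. Such referral is a co-intervention that could affect the distress outcomes.

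**Working it through.** The plan gives no figure to reproduce. The check traces each item named in the trigger to the instrument and visit where the documents place it.

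| Element of the trigger | Baseline | 6 weeks | 3 months | 6 months |
|---|---|---|---|---|
| Suicide-ideation item identified | Yes (question 30) | None | None | None |
| Substance-abuse item identified | None | None | None | None |

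Suicide ideation: identified at 1 of 4 time points, and at 0 of 3 follow-up visits. Substance abuse: identified at 0 of 4.

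Next, the other routes by which a randomised participant could reach referral during follow-up:

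- **Voicing to the Coordinator.** The text limits this to enrollment, so it does not extend to follow-up in either arm.
- **Voicing to the Counselor.** The text limits this to the intervention. Section IV.C says the Counselor only delivers the intervention and takes no part in data collection, so this route exists in the stepped-care arm alone.
- **The Arm 1 statement.** It promises referral of controls but gives no means or time of detection.
- **Contact while measures are collected.** Section IV.A allows completion online, on a mailed copy, by telephone with a graduate research assistant, or in person with the Coordinator when the assistants cannot locate the participant. Staff contact at a given visit is therefore possible but not assured. The crisis-referral training in the Referral Protocol names Coordinators and Counselors, not research assistants.

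Last, the number of planned assessments affected. Section IV.C expects 444 randomised participants, 222 per arm, with three follow-ups each.

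- No attrition: 444 × 3 = 1,332 in all; 222 × 3 = 666 in enhanced usual care.
- 20% attrition (Section IV.C: 356 remaining, 178 per arm), all of it before 6 weeks: 356 × 3 = 1,068 in all; 178 × 3 = 534 in enhanced usual care.
- 34% attrition (upper figure in Section IV.G), all of it before 6 weeks: 444 × 0.66 × 3 ≈ 879 in all; 222 × 0.66 × 3 ≈ 440 in enhanced usual care.

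These are assessments with no identified trigger item. They are not missed cases.

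**The case against.** A reader might infer that the trigger cannot work after randomisation, or that the question is no longer asked. The documents do not support that. The Referral Protocol itself says such items can be endorsed at any of the four points. The survey is described as attached but is not in the text available, and the PROMIS and HADS items are not printed. Table 1 lists outcomes, and a safety item need not appear in an outcome table. An item may exist and simply not be named. This part of the objection stands in full. The text also says any of the four assessments, so endorsement at every visit is not required.

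Control-arm referral is not ignored, since the Arm 1 description provides for it. Coordinators trained in the hospital's crisis protocol may meet some controls when collecting measures. The Counselor advantage is also uneven, because Step 1 participants have an orientation session and then active monitoring only. These points narrow the difference between arms. They do not close it, because none says how a control with new ideation is to be found.

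Exclusion criterion (c) can be read as covering only ideation that might interfere with consent or participation. It would then be wrong to say that every baseline endorser is excluded. The baseline question also serves the non-randomised group.

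A reader might further infer that a comparison of suicidality or referrals between arms is spoiled. No such comparison is planned, so the statistical harm is a possible effect of unequal referral on distress and not a damaged endpoint. Nor do the documents give an incidence of new ideation, so no number of affected people can be estimated.

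**Conclusion.** The concern holds as a conflict between a stated participant protection and the assessment content described elsewhere. If follow-up is run as Section IV.A describes it, the trigger has no identified item to act on at 6 weeks, 3 months or 6 months. For substance abuse it has none at baseline either. The gap is wider in enhanced usual care, where no named item or contact covers follow-up and only a general promise of referral remains.

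The extent is 0 of 3 follow-up visits for suicide ideation and 0 of 4 time points for substance abuse. That is roughly 880 to 1,330 planned follow-up assessments, of which about 440 to 670 are in enhanced usual care, depending on attrition. The conclusion rests on the protocol text alone. If the attached survey or the repeated scales contain suitable items at follow-up, the fault reduces to a failure to designate them. It is still worth correcting, because staff need to know which answers trigger referral.

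**What to change.** Reconcile Table 1 and the baseline survey description in Section IV.A, the numbered exclusion questions in Section IV.B, and the Arm 1 description and Referral Protocol in Section IV.C, so that the stated trigger can operate at 6 weeks, 3 months and 6 months in both arms:

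1. In the Referral Protocol, cite by instrument and number the suicide-ideation and substance-abuse items that serve the trigger at each of the four assessments.
2. Where no existing follow-up item does so, carry the plan's own baseline items into the follow-up assessments, for patients and caregivers in both arms.
3. State in the Arm 1 description how and when controls come under the same trigger.
4. Tabulate endorsements and resulting referrals by arm and visit for the DSMB.

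The referral rule and the hospitals' own protocols are left as they are. The cost is an amendment, possibly a few added items per visit, and one further DSMB table. If suitable items are already in use, only the citations and the table are needed.
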